Hypothesis 2: The EX intervention will lead to improved secondary outcomes of VIPN (lower P-CIN scores), Neuropathic pain (lower NPS and CTCAE scores), Quality of Life (higher Peds QL V4 scores), and Physical activity (higher total activity time, more time with higher heart rate throughout the day, more exercises completed, and higher oxygen consumption) for patients at the end of the intervention (T2) compared to baseline (T1).

Hypothesis 3: The EX intervention will lead to increases in Biomarkers of NGF, SNAP1, GAP 43, and PDGF-BB and Chemerin at the end of the intervention (T2) compared to baseline (T1).

Hypothesis 4: Changes in key predictor variables (e.g. self-efficacy, outcome expectations, support) will be associated with changes in outcomes (e.g. neuropathy, pain, and quality of life).

C. BACKGROUND & RATIONALE

Vincristine-induced peripheral neuropathy (VIPN)

The most diagnosed pediatric cancer (ages 0-19) is leukemia (26%) with acute lymphoblastic leukemia (ALL) being the most common (75%)⁷, while lymphoblastic lymphoma (LL) is a fast-growing type of Non-Hodgkins Lymphoma (NHL) accounting for 2% of all NHLs¹³. Patients with both ALL and LL receive Vincristine as part of their standard treatment plan utilizing the same treatment and dosing schedule¹³.

Due to improved multidrug treatment regimens over the past 40 years, the 5-year survival rate for these children has increased from 57% to 80% - 90%^{7,14}. However, **due to vincristine exposure, we know that approximately 78% of the children with ALL will develop severe peripheral neuropathy (Vincristine-induced peripheral neuropathy: VIPN)**⁵. To date there is no study on children with LL. VIPN is observed very early in treatment, usually within the first four weeks¹⁵. The development of VIPN is characterized by progressive motor, sensory and autonomic loss of function and usually results in dose reductions of vincristine during treatment and thus an overall loss of therapeutic efficacy¹⁶⁻¹⁸. While we know that methotrexate, another chemotherapeutic agent used in the treatment of ALL, can also have toxic effects, severe neuropathy induced by this drug is very rare (<1%) and manifests as a reversible optic neuropathy not a peripheral neuropathy^{19,20}.

Long-term health outcomes in survivors of childhood cancers

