The Fitbit activity tracker was chosen for this feasibility study due to its versatility and effectiveness within younger populations of children. The FitBit's ease of use, comfort, design and feedback features were important factors for all age groups (children and AYA). Researchers in some studies utilized the Fitbit activity tracker to assess adherence to home-based activity programs⁷⁵.

I. PROCEDURES

[figure not shown]
I.1 Overview

For this feasibility study, 40 pediatric patients with a diagnosis of ALL or LL who have a TNS of ≥ 3 at the end of four weeks of vincristine treatment will be enrolled from Riley Hospital for Children, Indiana University Health North Hospital, . Children and AYA will be recruited during their first four weeks after diagnosis and if they have a TNS ≥ 3 at the time of baseline (week 4-6 T1) they will be enrolled into the study. During T1 patients will complete all questionnaires, neuropathy exams, and provide blood samples and then again at week 14 (T2). Neuropathy exam may be performed during weeks 4 through 6 to accommodate regimented clinical visits. Exercise assessments will be performed on week 7. Subjects will check-in with the exercise therapist during weeks 9, 11, and 13 at a minimum, or once a week during the study if they choose (weeks 7-15). These in-

person sessions will take approximately 15 minutes, and the therapist will provide education, evaluate the subject's exercise plan, review exercises, set goals, and make plans to optimize adherence to the exercise program.

All study visits will take place before or after routine clinic visits so that patients and their families do not have to make additional trips to the four hospital sites. EX sessions will be completed by patients at home using instructional videos that will be given to participants during their study orientation.

I.2 Intervention timeline

I.3 Exercise (EX) Intervention

The EX intervention will include both an in-person exercise schedule and at-home video EX sessions (See Appendix I and II). The EX intervention will be designed and led by an AFAA (Athletics and Fitness Association of America) certified physical fitness trainer with fifteen years' experience and a professional with a PhD in an Exercise Science related field.

In-Person Exercise Sessions:

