Pediatric Neuropathic Pain Scale (NPS) - Five: The Neuropathic Pain Scale (NPS) was designed to assess the distinct pain qualities associated with neuropathic pain. The NPS consists of 5 items which are rated on a scale of 0 to 10 (0="no pain" to 10="severe pain"). Each question examines an individual aspect of pain and is measured independently¹⁵. The rating scale is based on the Faces Pain Rating Scale – Revised (FPS-R) which is a self-report measure of pain intensity that was developed for children⁷⁹ (See Appendix VII and VIII).

The NCI Common Terminology Criteria for Adverse Events (CTCAE) V4.02: This scale grades adverse events occurring after chemotherapy in cancer patients and explores the quality of life (QOL) findings among post therapy cancer patients. The NCI CTCAE is a descriptive terminology that can be utilized for pain (Appendix IX) reporting and is required to be completed for all cancer studies⁸⁰.

Quality of Life

Pediatric Quality of Life Inventory (PedsQL 4.0): The PedsQL is a modular approach to measuring health-related quality of life in healthy children and those with acute and chronic health conditions. The PedsQL integrates generic core scales and disease-specific modules into one measurement system (Appendix X). The 23-item PedsQL generic core scales and disease-specific scales were designed to measure the core dimensions of health as delineated by the World Health Organization, as well as role (school) functioning. For the purpose of this study, we will only be utilizing the generic core scales section of the inventory. This measure is tailored to 5 different age groups: toddlers (2-4); children (5-7); children (8-12); teens (13-18); and young adults (18-2). The Child and Parent Reports (ages 5-7), Children (ages 8-12) and Teens (ages 13-18) are made up of 23 items comprising 4 dimensions: Physical functioning; Emotional functioning; Social functioning, and School functioning. Patient participants will complete the child-report questionnaire, and their parents will complete the parent-report version (See Appendix X).

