Ferrans & Powers Quality of Life Index: Total quality of life will be measured using the Ferrans and Powers Quality of Life Index Version III and is a 66-question index designed to evaluate social, psychological, family, and health satisfaction (See Appendix XI). This assessment is valid for ages 19 and above. Higher scores indicate greater satisfaction in quality of life with an internal Cronbach's alpha of 0.93⁸¹.

Social Learning Theory Questionnaire

Self-Efficacy: There is currently no exercise self-efficacy scale for children and AYA's with cancer. We have adapted the Bartholomew physical activity self-efficacy scale for children and AYA's for use in our study⁸². We have adapted the original self-efficacy scale by adding two questions that are specifically neuropathy related and replaced the term exercise where physical activity had been used. Responses to the questions are limited to Yes/No and not applicable. (See Section 1 Appendix XII).

Support: The support module was taken from a larger validated scale developed by Liang et al (2014) which measures physical activity self-efficacy, enjoyment, and exercise social support for children⁸³. The support section of the questionnaire consists of 10 questions rated on a 5 point scale from None to Very often. The items assess support children and AYA's receive from parents and peers to facilitate exercise. We have adapted the term physical activity to the term exercise for this study (See Section 2 Appendix XII).

Outcome Expectations: We adapted an existing exercise outcomes expectations questionnaire from the adult literature for the purposes of our study. The survey consists of 10 items targeting exercise outcome expectations. Patients are asked to rate each item on a 5 point scale. Items were edited for developmental level/appropriateness⁸⁴. (See Section 3 Appendix XII)

Physiological Parameters

[figure not shown]
Fitbit activity tracker: All patients will be instructed to wear their Fitbit activity trackers every day during waking hours throughout the intervention period. The Fitbit activity tracker (specifically the Charge 2) has a five-day battery life and an “always-on” heart rate tracking system. It is an accelerometer that is worn like a small wristband and records data on movement (steps, HR, distance and activity), total activity minutes, heart rate and total minutes of inactivity including sleep. The data is stored on the device and then can be downloaded wirelessly to a computer⁷⁵.

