Adherence will be measured by self-report of session completion (See Appendix III) and activity tracking via FitBit. All participants will be asked to fill out a short 5 question survey following their EX session regarding their workout, energy level, food intake, and sleep quality. Parents will be asked to initial and review the questions and add any additional comments they feel would be helpful for us to know. The Daily Log is designed not just to aid the child in planning and goal setting, but also to give parents an opportunity to provide positive reinforcement for the child's daily exercise. The patients will also be asked to hit a start EX button on the FitBit at the beginning of the intervention which shows that they have started the video and then hit it again upon completion. The instructor in the video will prompt the child to start and stop their FitBit as a reminder.

Acceptability

Patient Satisfaction Survey: This satisfaction survey was adapted from an existing exercise intervention satisfaction survey⁹⁰. The satisfaction survey consists of 13 items, and they will be asked to respond to each item using a 5 point scale. Patients will provide feedback on the exercise program, exercise videos and therapist support. There is also an open response question for additional feedback (See Appendix XIV).

Parent Satisfaction Survey: Parents will also be asked to complete a satisfaction survey regarding the exercise program, exercise videos, and therapist support. To assess the satisfaction of the parents/caregivers of pediatric cancer patients (peripheral neuropathy symptoms) while participating in an exercise intervention during the Consolidation Phase of chemotherapy⁹⁰. The satisfaction survey consists of 13 items, and they will be asked to respond to each item using a 5 point scale. (See Appendix XV)

Domain, Measurements and Schedule for Study Outcomes

Domain	Measure	# Items	Schedule	
			T1	T2
Predictors				
Demographics	Gender, age, race/ethnicity, pre-diagnosis exercise level		X	
Medical Characteristics	Neuropathy, Weight, ALL/LL diagnosis		X	
Physical Functioning	Baseline Standardized Fitness Assessment	13	X	
Self-efficacy	SLT Exercise Questionnaire	10	X	
Outcome Expectations	SLT Exercise Questionnaire	10	X	X
Support	SLT Exercise Questionnaire	10	X	X
Primary Outcome				
Feasibility	Percentage of subjects that can complete the 8-week intervention FitBit data Daily Log	6	Weeks 6-13	

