Acceptability	Patient Satisfaction Survey Parent Satisfaction Survey	13 13		X
Secondary Outcomes				
Physical Activity				
Total Activity Time during study	FitBit Tracker Daily Log	8		
Heart Rate	FitBit Tracker	NA	Weeks 6-13	
Exercise	Fitbit Tracker Daily Log	8		
Biomarkers				
Germline DNA Chemerin levels PDGF-BB levels IL-13 levels GAP 43 Synapsin NGF	Blood Draw	NA	X	X

Neuropathy

	NCI CTCAE Version 4.02	2		X
	Total Neuropathy Score - Pediatric Vincristine (TNS-PV)	25	X	X
	Total Neuropathy Score - Clinical (TNSc)	7	X	X

Pain

	P-CIN Pediatric Chemotherapy-Induced Neuropathy Patient Reported Outcome	13	X	X
	Pediatric Neuropathic Pain Scale - Five	6	X	X

Quality of Life

	Peds QL V4 Scale	23	X	X
	Ferrans and Powers	66	X	X

I.5 Blood Sample Collection

This study will include collection of a minimum of 15 mL of whole blood at 2 time points: baseline or pre-intervention (week 6) and post-intervention (week 14). Blood samples will be stored at -80°C until analysis for germline DNA, chemerin levels, NGF, SNAP1, GAP43 and cytokines PDGF-BB and IL-13. Whenever possible, blood will be drawn at the same time as blood is drawn for routine clinical purposes. Blood will always be drawn by trained technicians. Please refer to the Laboratory Manual for this study for blood collection, processing, transfer and storage instructions.

I.6 Data Processing and Storage

Survey Data: All survey study data collected will be stored in the Research Electronic Data Capture (REDCap) database. REDCap is managed through the Department of Biostatistics in the Indiana University School of Medicine. Access to the password-protected database will be limited to study personnel, and any data shared outside of the study team will be de-identified prior to distribution.

Fitbit Data: The Fitbit data will be automatically imported to a Fitbit application on the company's secure server and then uploaded automatically to an excel file. The data will be downloaded weekly to a password protected master excel file folder stored on a university secured server and managed by the Bioinformatics core (See human subjects section for further details). All physiological measures: Heart Rate, Steps, Distance and Activity, will be captured using the Fitbit Charge HR.

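### The schedule table takes CTCAE only at T2 and self-efficacy only at T1, so two planned T1–T2 change analyses have no pairs if sites follow it

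*Combined protocol and SAP*

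**What the plan says.** **CTCAE.** Section B, Aim 2, Hypothesis 2 includes "Neuropathic pain (lower NPS and CTCAE scores" among the outcomes expected to be better at T2 than at T1. Section J.2 analyses such outcomes with paired tests, effect sizes and repeated measures ANOVA, all of which need a T1 value. In the schedule table that closes section I.4, the row "NCI CTCAE Version 4.02" has 2 items, an empty T1 cell and a mark at T2.

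**Self-efficacy.** Hypothesis 4 states: "Changes in key predictor variables (e.g. self-efficacy, outcome expectations, support) will be associated with changes in outcomes". Section J.2 plans Pearson correlations of change scores and names self-efficacy first. The table has three rows for the "SLT Exercise Questionnaire". Outcome expectations and support are marked at both visits; self-efficacy is marked at T1 only. Section I.4 places self-efficacy in the same instrument as the other two scales ("See Section 1 Appendix XII", against "See Section 2 Appendix XII" for support).

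**Visit text.** Section I.1 says: "During T1 patients will complete all questionnaires, neuropathy exams, and provide blood samples and then again at week 14 (T2". It does not mention CTCAE. Section I.4 describes CTCAE in these terms: "This scale grades adverse events occurring after chemotherapy in cancer patients". It adds that CTCAE can be used to report pain and is required in cancer studies, but gives no time points.

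**The concern.** A change from T1 to T2 needs a value at each visit. For these two measures the table supplies one. A site working from the table would collect no baseline CTCAE grade and no follow-up self-efficacy score, and values missed at a scheduled visit may not be recoverable.

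Aim 2 exists to produce effect size estimates for a larger trial. With one time point there is no mean change, effect size or confidence interval to carry forward. The statement in section H.1 that a 0.5 SD difference is detectable for the other outcomes could not apply to CTCAE. Section I.7 names self-efficacy as the main construct behind the intervention, so losing its change score removes the most direct check of the conceptual model.

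Two smaller inconsistencies sit in the same hypotheses:

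- **Chemerin.** Hypothesis 3 lists chemerin among the markers that will increase. The opening of section B says exercise lowers it, and the Biomarkers paragraph of section E leaves it out of the markers expected to rise. This affects interpretation, not the test.
- **Oxygen consumption.** Hypothesis 2 names it as a T1–T2 outcome, but the supplied text gives no measure of it. The baseline fitness assessment includes aerobic fitness and is marked at T1 only. Section I.4 mentions T2 physiological assessments at week 15, in the description of the walk test. It is unclear whether the aerobic item is repeated then. The form, Appendix XIII, is in a separate file and was not seen.

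**Working it through.** **1. The plan's own figure (section H.1).** Inputs: 40 enrolled, 15% attrition, a 0.5 SD difference, paired t-test, two-sided α = 0.05.

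- Completers: 40 × (1 − 0.15) = 34.
- Power from the noncentral t distribution with n − 1 = 33 degrees of freedom and noncentrality 0.5 × √34 = 2.92, taking 0.5 SD as the SD of the change: 80.8%. The smallest n giving 80% is 34, and the smallest effect detectable with 80% power at n = 34 is 0.495 SD.
- Cross-check with the pilot SD: SD of change = 3.66 × √(2 × (1 − 0.4)) = 4.01. A 2-point change is 2 / 4.01 = 0.499 SD, with power 80.6%.

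The stated sample size and power reproduce.

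**2. Marks in the schedule table.**

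| Block | Rows | Both visits | One visit |
|---|---|---|---|
| Neuropathy, pain, quality of life | 7 (CTCAE, TNS-PV, TNSc, P-CIN, NPS-Five, PedsQL, Ferrans and Powers) | 6 | 1: CTCAE, T2 only |
| SLT questionnaire | 3 (self-efficacy, outcome expectations, support) | 2 | 1: self-efficacy, T1 only |

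**3. Available pairs among 34 completers.**

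| Measure | Sites follow the table | Sites follow I.1 |
|---|---|---|
| CTCAE | 0 | 0 to 34, depending on whether it counts as a questionnaire or neuropathy exam |
| Self-efficacy | 0 | up to 34 |

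**4. Consequence for the analyses.** With 34 pairs, CTCAE would have the 80.8% power of step 1 for a 0.5 SD change, if a paired t-test is suitable for it. With 0 pairs there is no test. For self-efficacy the planned analysis is a correlation, so that power figure does not describe it. With 0 change scores, no correlation involving self-efficacy change can be computed.

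**5. Is there a T1 CTCAE grade elsewhere?** The only other neuropathy grade is exclusion criterion 1 in section F.2. It refers to the time before any vincristine, so it is not a T1 value.

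**6. Could a mark have been lost in converting the PDF?** Two other single-visit rows read as they should. Acceptability has an empty T1 cell and a T2 mark, and J.2 places the patient satisfaction survey at the end of the study. The baseline fitness assessment is marked at T1 only. The CTCAE row has the same pattern as the acceptability row. A lost mark is possible but is the less likely reading.

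**The case against.** The strongest reply is that the rest of the protocol shows both measures were meant to be taken twice. Section I.1 repeats all questionnaires at T2, and self-efficacy is one section of a questionnaire whose other two sections are marked at T2. A site handing out the whole form would collect it. CTCAE sits in the table's neuropathy block beside TNS-PV and TNSc, so the neuropathy exams in I.1 could be read to include it. The table is also not a complete schedule: the six-minute walk test is described at T1 and T2 but does not appear in it. And the supplied table is visibly damaged. Block headings have come away from their rows, and two of the three Fitbit rows show no schedule.

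Much of this stands. It shows that the problem is a contradiction to reconcile, not proof that data will be lost. It is strong for self-efficacy and weaker for CTCAE, because nothing in the text names CTCAE at T1 and I.4 describes it as an adverse event scale. What it does not do is make the table right: the table conflicts with Hypotheses 2 and 4 and with J.2, and collection would depend on which page a site reads.

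It is also fair to say that the damage is bounded. NPS remains as a paired pain outcome, and Hypothesis 4 gives self-efficacy as one example, with outcome expectations and support still measured twice.

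**Conclusion.** The concern holds. As supplied, the schedule table does not support the CTCAE part of Hypothesis 2 or the self-efficacy part of Hypothesis 4. If sites follow it, both have 0 pairs out of 34; if they follow I.1, self-efficacy has up to 34 and CTCAE between 0 and 34.

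This rests on two assumptions: that the empty cells are in the source document, and that 34 participants complete as H.1 expects. Confidence is medium because of the first. The conflict should be corrected, but it does not threaten the main results: feasibility, acceptability, TNS-PV and the sample size are unaffected. The chemerin and oxygen-consumption points are accurate on the supplied text and minor.

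**What to change.** 1. In the schedule table, mark CTCAE at T1 and the self-efficacy section at T2.
2. Name CTCAE in section I.1 as done at both visits, so that text and table agree.
3. If either measure is not meant to be taken twice, remove its change analysis from Hypothesis 2 or 4 and from J.2.
4. State the expected direction for chemerin and make Hypothesis 3 agree with the opening of section B.
5. Name the oxygen-consumption measure and its two time points, or delete it from Hypothesis 2.

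The cost of items 1 and 2 is two table marks and a few words. In practice that is one 2-item grading at the existing T1 visit and one 10-item section of a questionnaire already given at T2. No new visit is needed and the sample size does not change. Items 4 and 5 are wording, unless the sponsor chooses to add an oxygen-consumption measurement.

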Exercise: EX increases oxygen to all organ systems, including the nervous system ¹⁰. Emerging data support the notion that EX protects against chemotherapy-induced peripheral neuropathy (CIPN) and may help repair damaged nerves after CIPN develops. Exact EX prescriptions have not yet been developed, but the more hours spent in moderate-to-vigorous activity, the less peripheral neuropathy experienced⁶⁸.

Oxygenation: The increase in oxygen which occurs during exercise (both aerobic and resistance) has been shown to increase NGF⁶⁹, SNAP1⁷⁰, and GAP 43¹¹ in rodent models of exercise. In addition, oxygenation enhances the pathway that increases Myelin Basic Protein (MBP), thus helping maintain myelin homeostasis⁷¹. Myelin is important for nerve conduction and is targeted during chemotherapy⁷², thus maintaining healthy myelin sheaths around the axons is necessary to minimize neuropathy.

Biomarkers: We have selected three key factors, NGF, SNAP1 and GAP 43 known to have a role in neuronal repair¹⁰ and one involved in myelination disease, PDGF-BB⁷³ to investigate in the current study. These factors should increase to compensate for any neuronal damage inflicted by the chemotherapy. In addition, we have data suggesting that the cytokine, IL-13 is also associated with VIPN⁴². In this instance, the higher the IL-13 plasma levels the worse the neuropathy, therefore we expect exercise to decrease this cytokine.

Quality of Life: Childhood and AYA cancer has a considerable negative effect on a child's physical wellbeing due to chemotherapy, radiation and the resultant side effects of each. Improving the symptoms that result from cancer treatment (e.g., VIPN) and decreasing symptom burden is related to improved quality of life in this population. Further, exercise has been shown to improve both muscle weakness and low cardiorespiratory fitness⁷⁴ for childhood and AYA cancer survivors, which may also improve their quality of life.

F. ELIGIBILITY CRITERIA

F.1 Inclusion criteria

Participants will be eligible for this study if they are:

- (1) age \geq 5 and \leq 25 years, (Riley Hematology/Oncology division accepts patients through age 25)
- (2) have been initially diagnosed with acute lymphoblastic leukemia (ALL), or lymphoblastic lymphoma (LL) and may also be a relapsed diagnosis,
- (3) will undergo the standard of care treatment for ALL or LL with vincristine.
- (4) will have a TNS-PV score of 3 or greater at week 6

F.2 Exclusion Criteria

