We plan to enroll 40 children and AYA who develop VIPN so that we will have at least 34 children and AYA who will complete the 14 week time point (assuming a 15% attrition rate based on this population). This study is sufficiently powered to detect a .5 SD difference in TNS-PV at the 14 week time point with 80% power based on a paired t-test with type I error set at .05. In a previous study of TPN-VS (Smith et al.) assessments from children with high severity VIPN resulted in TNS-PV of (n = 165 assessments from 14 children, mean = 8.02, SD = 5.22), for middle severity (n = 559 assessments from 70 children, mean = 4.22, SD = 3.01), and for low severity TNS-PV (n = 342 assessments from 25 children, mean = 1.94, SD = 1.86). Based on a pooled SD = 3.17 from these three groups, there is approximately a 1.9 SD difference in mean TNS-PV between the high and low severity groups, a 1.2 SD difference between the high and middle severity groups and a .7 SD difference between the middle and low severity groups. Thus if our children and AYA mimic the middle severity group prior to treatment we should be adequately powered to detect if our intervention is able to move them to low severity. Additionally, in pilot data (unpublished) TNS-PV at baseline (1 month) was 3.36 with SD = 3.66. With 34 children and AYA, we will have 80% power to detect a 2 point change in TNS-PV (which is considered clinically meaningful) assuming a SD = 3.66 at both time points and .4 correlation between time points with a paired t-test with type I error set at .05. For FACES (range 0 to 5), based on Smith et al, we estimate the pooled SD = .7 for high, middle, and low severity groups. With a sample size of 34, we are powered to detect a .35 mean difference in FACES, based on a paired t-test with type I error set at .05.

For other outcomes, which we do not have pilot data, we will still be able to detect a .5 SD difference in the mean based on a two-sided paired t-test with type I error set at .05. Even if we do not detect statistically significant differences in these outcomes in the proposed study, estimated means and SDs can be used for planning larger studies in the future.

H.2 Fitbit tracker justification

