To address Aim 1, adherence in the intervention group will be measured through a 5 question survey at each treatment and also through start/stop on the Fitbit. Adherence scores will be summarized across time with descriptive statistics (N, mean, SD, median, minimum, and maximum). From start/stop information, the proportion of exercise sessions completed and the proportion of patients which complete at least 50% of the exercise sessions along with associated 95% confidence intervals will be estimated. Additionally, descriptive statistics will be provided for the patient satisfaction survey provided at the end of the study.

To address Aim 2, we will use paired t-tests to examine change from baseline (T1) to 14 weeks (T2). For outcomes which are known to be non-normal such as biomarkers, we will use Wilcoxon-signed rank tests. We plan an intent-to-treat analysis. Even if we do not see significant differences, descriptive statistics including means, SD, and effect sizes (differences in means between the two time points divided by pooled SD) will be reported for outcomes along with 95% confidence intervals. All analysis will include checking of assumptions. Additionally, we will also use repeated measures ANOVA to estimate the contrast of interest (change from baseline at 14 weeks) for primary and secondary outcomes, after adjusting for age and baseline activity level.

For activity outcomes obtained from the FitBit, such as patients' daily number of steps, distance, active minutes, and heart rate, we will start with simple techniques such as paired t-tests or Wilcoxon signed-rank tests to compare the mean change in activity level from baseline (T1: summarized over week 6) to treatment end (T2: summarized over week 13). As an exploratory analysis, we will also use a generalized linear mixed model with appropriate distribution (e.g. Poisson) and link function fit to all weekly outcomes to examine changes over time using time as a continuous variable. We expect to have an abundance of information provided from the Fitbit, thus we will estimate descriptive statistics (N, mean, SD, median, minimum, and maximum) for all outcomes (i.e., number of steps, distance, active minutes, and heart rate) at each week to aid in planning future studies.

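### H.1 credits every outcome without pilot data with a detectable 0.5 SD, which takes about 34 pairs, but P-CIN (ages 5-17) and TNSc and Ferrans & Powers (19 and over) share no patient, so 40 enrolled cannot supply both sets.

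*Combined protocol and SAP*

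**What the plan says.** H.1 plans 40 enrolled so that "we will have at least 34 children and AYA who will complete the 14 week time point", allowing 15% attrition. It then makes three kinds of power statement, all for a paired t-test at 0.05:

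- **TNS-PV:** 80% power for 0.5 SD, and for a 2-point change "assuming a SD = 3.66 at both time points and .4 correlation between time points".
- **FACES:** "With a sample size of 34, we are powered to detect a .35 mean difference in FACES", with a pooled SD of 0.7. Neither the power nor the correlation is given.
- **Everything else:** "For other outcomes, which we do not have pilot data, we will still be able to detect a .5 SD difference in the mean". No power, sample size or SD unit is given, and no outcome is excepted.

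H.1 adds that, without significance, "estimated means and SDs can be used for planning larger studies in the future". J.2 plans paired T1-to-T2 tests for Aim 2 and defines the reported effect size as "differences in means between the two time points divided by pooled SD", with 95% confidence intervals.

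Eligibility in F.1 runs from 5 to 25 years ("Riley Hematology/Oncology division accepts patients through age 25"). I.4 gives the age range of each instrument: TNS-PV 5-25, P-CIN 5-17, TNSc 19-25, Ferrans & Powers 19 and above. The outcome schedule lists P-CIN, TNSc and Ferrans & Powers at both T1 and T2. The documents give no expected age split and no minimum number per age group.

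**The concern.** H.1 gives P-CIN and the 19+ instruments the same detectable effect as outcomes measured at every age. That figure uses all 34 expected completers, and the two groups of instruments draw on patients who do not overlap.

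Aim 2 exists to supply effect sizes for a later efficacy trial, and its Hypothesis 2 names P-CIN as the secondary VIPN measure. Read as written, a null result on P-CIN, TNSc or Ferrans & Powers could be taken as having about 80% power behind it when it may have far less.

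**Working it through.** **Inputs.** 40 enrolled and at least 34 completing; two-sided paired t-test at 0.05; effect 0.5 SD (all H.1). Power of 80% is carried over from the TNS-PV sentence. Age ranges are from I.4 and F.1.

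**Method.** Power comes from the noncentral t distribution with n − 1 degrees of freedom and noncentrality d√n, where d = mean change / SD of change.

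**1. The plan's own figures.**

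- Completers: 40 × 0.85 = 34.
- Power at d = 0.5: 79.5% with 33 pairs and 80.8% with 34. So 34 is the minimum.
- TNS-PV: SD of change = 3.66 × √(2 × (1 − 0.4)) = 4.01; d = 2/4.01 = 0.499; power at n = 34 is 80.6%. This reproduces, and it shows that 0.5 SD in H.1 fits SD of change as the unit.

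**2. Two sets with no patient in common.** P-CIN needs age 17 or below; TNSc and Ferrans & Powers need 19 or above. Two sets of 34 pairs require 2 × 34 = 68 patients, and 40 are enrolled.

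- If exactly 34 complete, any completer aged 18 or older takes P-CIN below 34.
- If all 40 complete, P-CIN keeps 34 pairs with up to 40 − 34 = 6 patients aged 18 or older. The 19+ instruments then have at most 6 pairs: 17% power, detectable effect 1.43 SD.
- The 19+ instruments reach 34 pairs only if all 34 completers, or 34 of 40 (85%), are 19 or older.

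**3. Size by number of pairs.** The age mix is unknown, so these are illustrations.

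| Pairs | Power for 0.5 SD of change | Detectable at 80% (SD of change) |
|---|---|---|
| 5 | 14% | 1.68 |
| 10 | 29% | 1.00 |
| 24 | 65% | 0.60 |
| 29 | 74% | 0.54 |
| 30 | 75% | 0.53 |
| 34 | 81% | 0.50 |
| 35 | 82% | 0.49 |

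With 5 completers aged 18 or older, P-CIN has 34 − 5 = 29 or 40 − 5 = 35 pairs. With 10, it has 34 − 10 = 24 or 40 − 10 = 30. The 19+ instruments have at most 5 or 10.

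**4. The SD unit.** In J.2's pooled-SD unit, with equal SDs at T1 and T2 and correlation r, the detectable effect at n = 34 is 0.495 × √(2(1 − r)): 0.59 at r = 0.3, 0.54 at 0.4, 0.50 at 0.49 and 0.44 at 0.6.

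**5. FACES.** SD of change = 0.7 × √(2(1 − r)).

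| r | SD of change | Power for 0.35 at n = 34 | Detectable at 80% |
|---|---|---|---|
| 0.3 | 0.828 | 67% | 0.41 |
| 0.4 | 0.767 | 73% | 0.38 |
| 0.49 | 0.707 | 80% | 0.35 |
| 0.6 | 0.626 | 89% | 0.31 |

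So 0.35 has 80% power only if r is about 0.49 or more. H.1 gives no r for FACES.

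**The case against.** **The impossibility depends on the unit and the power level.** The sentence on other outcomes states neither. In J.2's pooled-SD unit, both sets could have 80% power for 0.5 SD if the T1-T2 correlation were about 0.76 with a 17/17 split, or about 0.71 with 20/20, and the documents do not rule that out. However, H.1 assumes 0.4 for TNS-PV, and its worked case fits SD of change. At 0.4 the pooled-SD reading makes the claim weaker (0.54 SD at n = 34).

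**P-CIN may fall under the FACES sentence.** Its items use a 6-point Faces scale, which fits H.1's 0-to-5 range. That is possible, but the FACES sentence states n = 34 outright, so the same age limit applies.

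**The P-CIN shortfall may be nil.** This stands. Thirty-four is a floor for completers, and up to six patients aged 18 or older cost nothing if all 40 complete.

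**The consequence is small.** Much of this stands too. TNS-PV covers ages 5-25, TNSc and Ferrans & Powers appear in no named hypothesis, and H.1 and J.2 rely on estimates and confidence intervals whether or not a test is significant. A small number of pairs would show as a wide interval.

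**Conclusion.** The concern holds. H.1's single detectable effect cannot be true of both P-CIN and the 19+ instruments, whatever the age mix among 40 patients. This takes 80% power and SD of change as the unit; H.1 states the first for TNS-PV, and its TNS-PV arithmetic fits the second.

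The size depends on an age split that the documents do not give. For P-CIN it runs from nothing to a modest loss (0.60 SD at 24 pairs). For TNSc and Ferrans & Powers it is large unless most of the sample is 19 or older. The primary feasibility outcome and TNS-PV are unaffected, so this is a figure to correct and not a flaw in the design. The missing SD unit and the missing FACES correlation are gaps in reporting; neither is shown to be an error.

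**What to change.** Revise H.1 as follows.

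1. Limit the 0.5 SD statement to outcomes measured in all completers, and give its power and its unit (SD of change). Add that in J.2's pooled-SD unit n = 34 detects 0.50 SD at a correlation of about 0.49 and 0.54 SD at 0.4, so that the two sections can be compared.
2. For P-CIN, give detectable effects over a range of age-eligible pairs, for example 0.60 SD at 24, 0.54 at 29, 0.53 at 30 and 0.50 at 34. For TNSc and Ferrans & Powers, either give a similar range or say that no detectable effect is claimed and that they are descriptive, read from J.2's estimates and intervals.
3. State the correlation behind the FACES figure of 0.35, or give 0.38 at a correlation of 0.4. Say whether FACES stands for P-CIN; if it does, replace n = 34 with the range in item 2.

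The cost is a few lines of text and less favourable stated figures for the age-limited outcomes, possibly including FACES. Enrolment, the feasibility outcome, TNS-PV power and the J.2 analyses stay as they are.
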